3.1.11 Left ventricular ejection fraction  $\geq$  institutional LLN

3.1.12 Ability to understand and the willingness to sign a written informed consent.

3.1.13 Must have a life expectancy  $\geq 16$  weeks

### 3.2 Exclusion Criteria

3.2.1 Prior therapy with PARP inhibitor, including olaparib

3.2.2 Prior therapy with trabectedin

---

- 3.2.3 Other malignancy unless curatively treated with no evidence of disease for  $\geq 2$  years except: adequately treated non-melanoma skin cancer, curatively treated in situ cancer of the cervix, ductal carcinoma in situ (DCIS), Stage 1, grade 1 endometrial carcinoma.
- 3.2.4 Current pregnancy or breast feeding. Pregnant women are excluded because the teratogenicity of both trabectedin and olaparib are unknown. Because there is an unknown risk to nursing infants from treatment of the mother trabectedin and/or olaparib, breastfeeding should be discontinued.
- 3.2.5 Known hypersensitivity to trabectedin or olaparib or any of the excipients of the products
- 3.2.6 Patients with symptomatic uncontrolled brain metastases. A scan to confirm the absence of brain metastases is not required. The patient can receive a stable dose of corticosteroids before and during the study as long as these were started at least 4 weeks prior to treatment. Patients with spinal cord compression unless considered to have received definitive treatment for this and evidence of clinically stable disease for 28 days.
- 3.2.7 Patients considered a poor medical risk due to a serious, uncontrolled medical disorder, non-malignant systemic disease or active, uncontrolled infection. Examples include, but are not limited to, uncontrolled ventricular arrhythmia, recent (within 3 months) myocardial infarction, uncontrolled major seizure disorder, unstable spinal cord compression, superior vena cava syndrome, extensive interstitial bilateral lung disease on High Resolution Computed Tomography (HRCT) scan or any psychiatric disorder that prohibits obtaining informed consent.
- 3.2.8 Resting ECG indicating uncontrolled, potentially reversible cardiac conditions, as judged by the investigator (eg., unstable ischemia, uncontrolled symptomatic arrhythmia, congestive heart failure, QTcF prolongation  $>500$  ms, electrolyte disturbances, etc.), or patients with congenital long QT syndrome.
- 3.2.9 Persistent toxicities ( $>$ Common Terminology Criteria for Adverse Event (CTCAE) grade 2) caused by previous cancer therapy, excluding alopecia.
- 3.2.10 Patients with myelodysplastic syndrome (MDS) /acute myeloid leukemia (AML) or with features suggestive of MDS/AML
- 3.2.11 Patients unable to swallow orally administered medication and patients with gastrointestinal disorders likely to interfere with absorption of the study medication.
- 3.2.12 Immunocompromised patients, e.g., patients who are known to be serologically positive for human immunodeficiency virus (HIV).
- 3.2.13 Patients with known active hepatitis (i.e. Hepatitis B or C).
- 3.2.14 Patients receiving any systemic chemotherapy or radiotherapy (except for palliative reasons) within 3 weeks prior to study treatment
- 3.2.15 Concomitant use of known strong CYP3A inhibitors (e.g. itraconazole, telithromycin, clarithromycin, protease inhibitors boosted with ritonavir or

cobicistat, indinavir, saquinavir, nelfinavir, boceprevir, telaprevir) or moderate CYP3A inhibitors (e.g. ciprofloxacin, erythromycin, diltiazem, fluconazole, verapamil). The required washout period prior to starting study treatment is 2 weeks.

- 3.2.16 Concomitant use of known strong (e.g. phenobarbital, enzalutamide, phenytoin, rifampicin, rifabutin, rifapentine, carbamazepine, nevirapine and St John's Wort) or moderate CYP3A inducers (eg. bosentan, efavirenz, modafinil). The required washout period prior to starting study treatment is 5 weeks for enzalutamide or phenobarbital and 3 weeks for other agents.
- 3.2.17 Major surgery within 2 weeks of starting study treatment and patients must have recovered from any effects of any major surgery.
- 3.2.18 Participation in another clinical study with an investigational product administered in the last 30 days prior to anticipated study treatment.
- 3.2.19 Judgment by the investigator that the patient should not participate in the study if the patient is unlikely to comply with study procedures, restrictions and requirements.
- 3.2.20 Has received a live vaccination with 2 weeks of enrollment.
- 3.2.21 Previous allogeneic bone marrow transplant or double umbilical cord blood transplantation
- 3.2.22 Involvement in the planning and/or conduct of the study
- 3.2.23 Previous enrollment in the present study

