**STUDY SCHEMA**

**STUDY SYNOPSIS**

Title	Phase II Multi-Center Trial of Trabectedin in Combination with Olaparib in Advanced Unresectable or Metastatic Sarcoma
Phase	Phase II
Methodology	Uncontrolled, Open label, Single-arm
Study Duration	3 years
Study Center(s)	Multi-center: 2 centers
Objectives	
Primary Objective:
 
a. To estimate the overall response rate (ORR) of combined trabectedin and olaparib in patients with advanced unresectable or metastatic sarcoma using a primary endpoint of complete + partial response as defined by RECIST 1.1.
 
Secondary Objectives:
 
a. To estimate the median progression-free survival (PFS) and 6-month PFS as defined by RECIST 1.1
 
b. To estimate the median, 1- and 2-year overall survival (OS)
 
c. To describe the safety and tolerability of combined trabectedin and olaparib
 
Exploratory Objectives:
 
a. To characterize next generation sequencing (NGS) findings on available reports from archival tumor samples to identify predictors of clinical response to therapy.
 
b. To evaluate expression of DNA damage repair pathways by IHC in available archival tumor samples and correlate with response to therapy
 
c. To assess the impact of treatment on levels of novel cardiovascular biomarkers, and determine whether levels predict cardiotoxicity

Number of Subjects	
This study will be conducted using a Simon Minimax two-stage design, with an interim analysis for efficacy to be performed after first stage.
 
Cohort 1 (LMS/LPS): First stage – 16 patients, Second stage – additional 10 patients
 
Cohort 2 (other sarcoma histologies): First stage – 13 patients, Second stage – additional 14 patients

Key Inclusion Criteria	
 
• Age <math>\geq</math> 16 years
 
• Advanced unresectable or metastatic sarcoma
 
• Received at least 1 prior standard chemotherapy. For cohort 1 patients, this must have included a prior anthracycline.
 
• Measurable disease by RECIST 1.1
 
• Adequate hematologic, renal, hepatic function
 
• Adequate creatine phosphokinase
 
• ECOG performance status <math>\leq</math> 1
 
• LVEF <math>\geq</math> institutional LLN
 
• Women of childbearing age and men must agree to use adequate contraception from signing informed consent to at least 6 months (females) and 5 months (men) after study drug treatment
 

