### 3.1 Inclusion Criteria

- 3.1.1 Advanced unresectable or metastatic sarcoma
  - Cohort 1: LMS/LPS
  - Cohort 2: Other histologies (excluding Gastrointestinal Stromal Tumors)
- 3.1.2 Must have received at least 1 prior standard systemic therapy regimen. For cohort 1 patients, this must have included a prior anthracycline.
- 3.1.3 Measurable disease by RECIST 1.1 criteria
- 3.1.4 Age  $\geq$  16 years
- 3.1.5 ECOG  $\leq$  1
- 3.1.6 Adequate hematologic, renal and hepatic function within 14 days prior to administration of study treatment as defined below:

Hemoglobin	$\geq 10$ g/dL with no blood transfusion within 28 days
Absolute neutrophil count	$\geq 1.5 \times 10^9$ /L
Platelets	$\geq 100 \times 10^9$ /L

Total Bilirubin	$\leq 1.5 \times$ institutional upper limit of normal (ULN).  NOTE: patients with elevated bilirubin secondary to Gilbert's disease are eligible to participate ( $<2.0 \times$ ULN should be used)
Aspartate aminotransferase (AST) & alanine aminotransferase (ALT)	$\leq 2.5 \times$ institutional ULN unless liver metastases are present in which case AST and ALT must be $\leq 5 \times$ ULN
Serum creatinine	Estimated or calculated creatinine clearance (Cockcroft-Gault formula) $\geq 51$ mL/min using the Cockcroft-Gault equation or based on a 24-hour urine test:  Estimated creatinine clearance = $(140 - \text{age} [\text{years}]) \times \text{weight} (\text{kg}) \times F^a$ serum creatinine (mg/dL) $\times 72$ a where F=0.85 for females and F=1 for males.

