Anticoagulant therapy	Patients who are taking warfarin may participate in this trial; however, it is recommended that international normalized ratio (INR) be monitored carefully at least once per week for the first month, then monthly if the INR is stable. Subcutaneous heparin and low molecular weight heparin are permitted.
Palliative radiotherapy	Palliative radiotherapy may be used for the treatment of pain at the site of bony metastases that were present at baseline, provided the investigator does not feel that these are indicative of clinical disease progression during the study period. Study treatment should be discontinued for a minimum of 3 days before a patient undergoes therapeutic palliative radiation treatment. Study treatment should be restarted within 4 weeks as long as any bone marrow toxicity has recovered.

Medication/class of drug:	Usage (including limits for duration permitted and special situations in which it's allowed):
Administration of other anti-cancer agents	Patients must not receive any other concurrent anti-cancer therapy, including investigational agents, while on study treatment. Patients may continue the use of bisphosphonates or denosumab for bone disease and corticosteroids for the symptomatic control of brain metastases provided the dose is stable before and during the study and they were started at least 4 weeks prior to beginning study treatment.

Primary prophylaxis with Granulocyte colony-stimulating factor (G-CSF) is not recommended, however, if a patient develops febrile neutropenia, study treatment should be stopped and appropriate management including G-CSF should be given according to local hospital guidelines. Please note that G-CSF should not be used within at least 24 h (7 days for pegylated G-CSF) of the last dose of study treatment unless absolutely necessary.

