### 6.2 Time and Events Table

All screening labs must be performed within 14 days prior to registration unless otherwise stated. Baseline imaging must be obtained within 28 days prior to registration.

	Screening*	Cycle 1 Day 1	Day 1 All Cycles n	Day 8, Cycles 1 and 2** n	Day 15 All Cycles n	Off Treatment n	Follow -Up m
Olaparib a		X	X-----	X-----	X-----		
Trabectedin		X	X				
Informed Consent	X						
History, vitals and PE	X	X	X			X	
Height & Weight b							
ECOG Performance Status	X	X	X			X	
ECG	X						

Concomitant medication review	X	X	X				
Toxicity Evaluations		X	X-----X				
Tumor Measurements c	X		X c			X	
CBC w/diff, PLT d	X	X	X	X	X	X	
Serum Chemistry e	X	X	X	X	X	X	
APTT, INR f	X						
Creatine phosphokinase	X	X	X			X	
Urinalysis g	X						
B-HCG h	X	X	X			X	
Transthoracic echocardiogram i	X		X i (every 3 cycles)				
Cardiovascular Biomarkers j	X		X j (C3D1 only)				
Archival Tissue k	X						
Bone marrow or blood cytogenetic samples l							

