- i. Transthoracic echocardiogram (TTE) will be obtained at baseline to ensure adequate LVEF. Repeat TTE will be obtained every 3 cycles ( $\pm 1$  cycles) while on trabectedin or if clinical concern of decline in ejection fraction. MUGA can be performed if inadequate assessment by TTE per standard practice.
- j. Assessment of cardiovascular biomarkers including suPAR, BNP, high-sensitive troponin-I and high-sensitivity CRP will be obtained at baseline and after 2 doses of trabectedin on cycle 3 day 1.
- k. Results of NGS (if available) and archival tumor tissue to test for the presence of alterations in DNA repair pathways. Patients will not be asked to undergo an additional biopsy to obtain tumor sample. Full reports must be provided by the investigator for documentation on the Patient Safety database. These data are not required to be entered into CRF.
- l. Bone marrow or blood cytogenetic samples may be collected for patients with prolonged hematological toxicities at any timepoint as clinically indicated as defined in Section 5.2. Bone marrow analysis should include an aspirate for cellular morphology, cytogenetic analysis and flow cytometry, and a core biopsy for bone marrow cellularity. If it is not possible to conduct cytogenetic analysis or flow cytometry on the bone marrow aspirate, then attempts should be made to carry out the tests on a blood sample.
- m. Patients will be followed every 3 months via phone for documentation of progression and survival status for a minimum of 2 years from registration. If patient is unavailable, then survival status will be determined if possible, by public available information.
- n. Visits on day 1 of each cycle, lab measurements at days 1, 8 and 15 of each cycle, and the end of treatment visit, can be completed  $\pm 3$  days.

\* Screening labs to be obtained within 14 days of initiation of therapy. Baseline imaging to be obtained within 28 days of initiation of therapy.

\*\* Laboratory assessment will be done on day 8 for first 2 cycles to monitor for cytopenias.

Continued day 8 laboratory assessment beyond cycle 2 is at the discretion of the treating physician.

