#### 7.1.3 Guidelines for Evaluation of Measurable Disease

All measurements should be recorded in metric notation, using calipers if clinically assessed. All baseline evaluations should be performed as close as possible to the treatment start and never more than 4 weeks before the beginning of the treatment.

The same method of assessment and the same technique should be used to characterize each identified and reported lesion at baseline and during follow-up. Imaging based evaluation should always be done rather than clinical examination unless the lesion(s) being followed cannot be imaged but are assessable by clinical exam.

**Clinical lesions:** Clinical lesions will only be considered measurable when they are superficial and >10mm diameter as assessed using calipers (e.g. skin nodules). For the case of skin lesions, documentation by color photography including a ruler to estimate the size of the lesion is suggested. As noted above, when lesions can be evaluated by both clinical exam and imaging, imaging evaluation should be undertaken since it is more objective and may also be reviewed at the end of the study.

**Chest X-ray:** Chest CT is preferred over chest X-ray, since CT is more sensitive than X-ray, particularly in identifying new lesions. However, lesions on chest X-ray may be considered measurable if they are clearly defined and surrounded by aerated lung.

**CT, MRI:** CT is the best currently available and reproducible method to measure lesions selected for response assessment. This guideline has defined measurability of lesions on CT scan based on the assumption that CT slice thickness is 5mm or less. When CT scans have slice thickness greater than 5 mm, the minimum size for a measurable lesion should be twice the slice thickness. MRI is also acceptable in certain situations (e.g. for body scans).

**Ultrasound:** Ultrasound is not useful in assessment of lesion size and should not be used as a method of measurement. If new lesions are identified by ultrasound in the course of the study, confirmation by CT or MRI is advised. If there is concern about radiation exposure at CT, MRI may be used instead of CT in selected instances.

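### The entry interval for prior therapy omits marketed non-chemotherapy anticancer drugs, and no rule puts the baseline scan after the last prior dose, so prior-drug effect can count as response.

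*Combined protocol and SAP*

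**What the plan says.** **Prior treatment required.** Section 3.1.2: "Must have received at least 1 prior standard systemic therapy regimen". The synopsis is narrower: "Received at least 1 prior standard chemotherapy". Both add a prior anthracycline for cohort 1 only. No inclusion criterion requires progression on the earlier regimen.

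**Interval before entry.** Exclusion 3.2.14: "Patients receiving any systemic chemotherapy or radiotherapy (except for palliative reasons) within 3 weeks prior to study treatment". Exclusion 3.2.18 adds "Participation in another clinical study with an investigational product administered in the last 30 days prior to anticipated study treatment". Exclusion 3.2.16 sets washouts for CYP3A inducers, which catches enzalutamide because of its interaction rather than because it is an anticancer drug.

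**During treatment.** The prohibited-medication table in 5.3 lists chemotherapy, immunotherapy, hormonal therapy (replacement therapy excepted), non-palliative radiotherapy, biological therapy and other novel agents as anticancer therapy. The restricted-medication table adds: "Patients must not receive any other concurrent anti-cancer therapy, including investigational agents, while on study treatment". Both rules apply on study treatment only.

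**Baseline scan.** The text above the table in 6.2 says "Baseline imaging must be obtained within 28 days prior to registration", and footnote c also counts from registration. The asterisk footnote to the same table says "Baseline imaging to be obtained within 28 days of initiation of therapy". Section 7.1.3 asks for baseline evaluations as near to treatment start as possible and "never more than 4 weeks before the beginning of the treatment".

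**Response.** Section 7.1.4.1 defines partial response as a decrease of at least 30% from the baseline sum of diameters.

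**The concern.** In a single-arm trial the whole change from baseline is credited to the study drugs. That is sound only if the baseline scan shows the disease after earlier treatment has ended and its effect has largely passed. The written rules do not ensure this, in two ways.

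First, the list of drugs that qualify a patient for entry is wider than the list of drugs that must have been stopped for a stated time. The plan treats immune, hormonal and biological agents as anticancer therapy once the patient is on study, but sets no interval for the marketed ones beforehand. This matters most in cohort 2, which takes many histologies and needs no prior anthracycline.

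Second, the imaging window is longer than the chemotherapy interval, so the scan can come before the last prior dose.

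The response thresholds are low (5 of 26 and 4 of 27), so one or two responses owed to the previous drug could change a cohort's conclusion.

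**Working it through.** **1. Which prior drugs have a stated interval (3.2.14, 3.2.16, 3.2.18)**

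| Last prior treatment | Stated interval before study treatment |
|---|---|
| Systemic chemotherapy or radiotherapy (palliative exception) | 3 weeks |
| Investigational product in another study | 30 days |
| Enzalutamide (as a CYP3A inducer) | 5 weeks |
| Other marketed immune, hormonal, biological or non-chemotherapy agent | none, unless it is a listed CYP3A inhibitor or inducer |

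A drug in the last row can satisfy 3.1.2 as the qualifying regimen.

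**2. Scan against last dose**

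- Earliest scan, counted from treatment start (6.2 asterisk footnote; 7.1.3): day −28.
- Chemotherapy interval (3.2.14): 21 days.
- Largest lead of scan over last chemotherapy: about 28 − 21 = 7 days. Example: a scan on day −28 and chemotherapy on day −22 are both within the limits, with the dose 6 days after the scan.
- For a drug with no stated interval the lead can approach 28 days.

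**3. The plan's own operating characteristics (11.2)**

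Inputs: cohort 1 null 9%, target 25%, stop at 1 or fewer of 16, promising at 5 or more of 26. Cohort 2 null 5%, target 20%, stop at 0 of 13, promising at 4 or more of 27.

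P(promising | p) = Σ over x > r₁ of P(X₁ = x) × P(X₂ ≥ k − x), where X₁ ~ Bin(n₁, p), X₂ ~ Bin(n₂, p), r₁ is the stage-1 stopping count and k the final threshold.

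- Cohort 1 at p = 0.09, terms for x = 2, 3, 4, 5, 6, 7: 0.0140 + 0.0270 + 0.0235 + 0.0091 + 0.0017 + 0.0002 ≈ 0.0756 (the terms are rounded). At p = 0.25: 0.8029.
- Cohort 2 at p = 0.05, terms for x = 1 to 5: 0.0106 + 0.0170 + 0.0110 + 0.0028 + 0.0003 ≈ 0.0416. At p = 0.20: 0.8011.

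Both meet the stated limits (10% and 5%) and 80% power. The design figures are not in dispute.

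**4. Illustration: the same rules with a higher null rate**

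The lift is assumed; the documents give no value for carry-over.

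| Assumed lift | Cohort 1 null → P(promising) | Cohort 2 null → P(promising) |
|---|---|---|
| 0 points | 9% → 0.076 | 5% → 0.042 |
| 1 point | 10% → 0.107 | 6% → 0.072 |
| 2 points | 11% → 0.145 | 7% → 0.111 |

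The stated limits are reached at null rates of about 9.8% and 5.3%, that is, lifts of about 0.8 and 0.3 points. A 2-point lift corresponds to 0.02 × 26 = 0.52 and 0.02 × 27 = 0.54 extra responders per cohort on average.

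**The case against.** **The lift is invented, and any Simon design is sensitive to its null rate.** This stands. The documents do not say how many patients will arrive from non-chemotherapy drugs, be dosed after the scan, or shrink by 30% because of it. The 9% and 5% benchmarks may contain similar carry-over, in which case the excess could be nil.

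**Direction is not fixed.** An early scan can also understate response, because growth between scan and first dose counts against the required 30% decrease. This stands: a reader might infer that the response rate will be inflated, but the documents show only that the rules permit it.

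**7.1.3 already asks for scans close to treatment start.** True, and it makes a day −28 scan less likely. But it sets no order relative to the last prior dose, and its hard limit is still 4 weeks.

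**A longer gap is tempting.** Counting the scan window from registration and adding 14 business days to first dose (5.1; up to 20 calendar days, holidays ignored) suggests 28 + 20 = 48 days before treatment. The asterisk footnote in 6.2 and 7.1.3 cap the window at 28 days or 4 weeks before treatment, so 48 days does not comply with the plan as a whole. What remains is a conflict of anchors.

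**Toxicity.** A reader might infer that toxicity from the earlier drug will be charged to the combination on a similar scale. The documents limit this: 3.2.9 excludes persistent toxicity above grade 2, entry laboratory values must be adequate within 14 days, section 8.1 treats onset before first dose as pre-existing, and section 8.3.2 requires attribution. Grade 2 residual toxicity can still worsen after the first dose and be counted, but this is minor.

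**The synopsis lists only key criteria.** Section 3 is operative and registration is reviewed centrally, so the difference in the term for prior therapy is a wording conflict, not a likely cause of large enrolment error.

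**Conclusion.** The concern holds as a gap in the entry and imaging rules. A patient can meet every written criterion having recently taken a marketed non-chemotherapy anticancer drug, or having had chemotherapy after the baseline scan, and any resulting shrinkage would count toward the primary endpoint with no control arm to reveal it.

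The timing figures (a lead of up to about 7 days for chemotherapy, approaching 28 days for drugs with no stated interval) follow from the text. The size of any bias does not. The movement in false-positive chance shown above rests wholly on the assumed 1- to 2-point lift, and on the benchmarks not already containing the same carry-over. It shows that the margin before the stated error limits is small, not that they will be exceeded. The sample sizes and decision rules are sound as designed. The change is worth making because it is cheap and closes a route to bias that the written rules leave open.

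**What to change.** 1. In 6.2 footnote c and in 7.1.3, require the baseline scan to be taken after the last dose of any prior anticancer therapy.
2. Reconcile 3.2.14 with 3.1.2 and with the anticancer classes in the 5.3 prohibited-medication table, so that the entry rule addresses all prior systemic anticancer therapy. Since 5.3 does not name targeted agents, state explicitly whether they are included. Any interval for the added classes is for the sponsor to set.
3. Use one term for qualifying prior therapy in the synopsis and 3.1.2.
4. Use one anchor for the imaging window. The opening text and footnote c of 6.2 count from registration; the asterisk footnote and 7.1.3 count from treatment start.

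The cost is a wording amendment. A few patients would need a re-timed or repeat scan, and some might start later, depending on any interval the sponsor sets. Sample size, error rates and decision rules do not change.
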